5 INTERIM FUTILITY ANALYSIS

An unmasked interim analysis will be conducted for futility assessment by an independent Data Monitoring Committee when approximately 34 (50% of the total planned AC-determined) NMO/NMOSD attacks occur in this study. The assessment of futility will be based on predictive power, which is based on the average conditional power calculated using the observed treatment effect trend and associated variability at the time of interim analysis to predict the final study outcome. All available subjects at the time of interim data cut will be included in the futility analysis. Details are provided in Appendix 2.

To be consistent with the hypothesis testing of the primary efficacy analysis as described in Section 3.4.1.3, the primary efficacy endpoint, time (days) from Day 1 to onset of an AC-determined NMO/NMOSD attack on or before the end of RCP, will be analyzed in the AQP4-IgG seropositive cohort as well as the ITT population for the interim futility analysis. The events to be included in the futility analysis will follow the methods described in the Section 3.4.1.1.

For the AQP4-IgG seropositive cohort, the treatment effect will be assessed using a Cox proportional hazards model with treatment indicator (MEDI-551 or placebo) as an explanatory factor; whereas for the ITT population, the model will also include serostatus as an additional explanatory factor. Subjects who have completed the RCP without having an AC-determined NMO/NMOSD attack will be censored on the date of completing RCP (Day 197 visit date). Subjects who have discontinued from the RCP for reasons other than an AC-determined NMO/NMOSD attack will be censored on the day of discontinuation from RCP (discontinuation visit date). Subjects who are ongoing in the RCP will be censored on the date of interim data cut. The SAS PROC PHREG will be used to fit this Cox proportional hazards model.

The predictive power based on the empirical trend observed at the interim analysis will be calculated by

$$\Phi \left[\frac{Z(t) - \sqrt{t}Z_{\alpha/2}}{\sqrt{1-t}} \right],$$

where $Z(t)$ is the observed Z -statistic at the interim futility analysis, t is observed information fraction and $Z_{\alpha/2}$ is upper $\alpha/2$ *th* quantile from standard normal distribution, and $\alpha=0.05$ ([Lan et al., 2009](#)). The $Z(t)$ will be calculated by the square root of the chi-squared statistic obtained from the aforementioned Cox proportional hazard model for the AQP4-IgG seropositive cohort and the ITT population, respectively. The observed information fraction t will be calculated using the observed number of AC-determined attacks at the interim analysis (ITT or seropositive) divided by the planned total number of AC-determined attacks for RCP (eg, 67 AC-determined attacks in the ITT population and 57 AC-determined attacks in the AQP4-IgG seropositive cohort for RCP).

The study may be declared as “futile” if

- the calculated predictive power is < 20% in the ITT population; AND
- the calculated predictive power is < 20% in the AQP4-IgG seropositive cohort.

If the study is declared futile the primary endpoint analysis and key secondary endpoint analyses will be conducted and all other endpoints will be summarized.

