4.8.8 Data Monitoring Committee

An unmasked independent DMC will perform evaluations of safety and clinical outcome data at specified regular intervals throughout the study and make recommendations to the sponsor regarding further conduct of the study. The DMC will conduct an interim analysis for futility as described in the description of the interim analysis in Section 4.8.10.

The DMC will monitor drop-out and missing primary and secondary outcome data on a case by case basis. In addition, the DMC will assess the thoroughness of the screening for possible NMO/NMOSD attacks and the effectiveness of the masking.

The DMC will receive 'real time' reports of new NMO/NMOSD attacks and will review the adherence of the investigators and AC to the process of attack diagnosis and adjudication.

Additional details will be provided in a separate DMC charter.

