7. The impact of attacks with onset before the full pharmacodynamic effect of MEDI-551 has been reached will be evaluated. Subjects with AC-determined attacks with onset on or before Day 15 will be censored at the time of the attack.
8. Analysis similar to primary analysis including AC-determined attacks up to and including January 27, 2017, remaining subjects will be censored on January 27, 2017 (the Sponsor received a recommendation from IDMC to stop enrollment and conclude the RCP of the study as early as January 27, 2017).

Consistency of treatment effect observed in Japanese subjects with global treatment effect may be assessed by the ratio of hazard ratios (HR) as $HR(\text{Japan})/HR(\text{Global})$, where respective HR estimate is obtained from Cox proportional hazards model based on respective population.

Table 3.4.1.4-1 Protocol-defined Criteria for an NMO/NMOSD Attack with criteria based severity

Attack Type	Protocol-defined Attack Criteria (with severity grading)

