Appendix 2 Details of Futility Analysis

An unmasked interim analysis will be conducted for futility assessment by the IDMC when approximately 50% of the total planned AC-determined NMO/NMOSD attacks occur in this study. This will be triggered when approximately 34 AC-determined NMO/NMOSD attacks occur in the ITT population. The assessment of futility will be based on predictive power, which is based on the average conditional power calculated at the observed treatment effect at the time of the interim analysis. The study will be considered futile if the predictive power is < 20% in both the ITT population AND the AQP4-IgG seropositive cohort. Figure 7-6 provides estimated predictive power when observed treatment effect varies from 0 to 90% in relative reduction in risk of an AC-determined NMO/NMOSD attack in the ITT population. The 20% predictive power translates into a treatment effect of approximately 27%. A value of 50% and 90% predictive power will result in 43% and 60% treatment effects, respectively, which are minimally detectable treatment effect and target treatment effect for this study. The actual predictive power will be calculated based on observed data.

[figure not shown]

Figure 7-6 Estimated Predictive Power Against Observed Interim Treatment Effect When 50% of AC-determined NMO/NMOSD Attacks are Available

AC = Adjudication Committee; HR = hazard rate; NMO/NMOSD = neuromyelitis optica/neuromyelitis optica spectrum disorders

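### The interim futility statistic has no sign, so an observed ITT hazard ratio above about 1.4 escapes the 20% predictive-power criterion

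*SAP*

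**What the plan says.** SAP Section 5 plans an unmasked futility look at about 34 of the 67 planned adjudicated attacks. It introduces the formula with "The predictive power based on the empirical trend observed at the interim analysis will be calculated by". The formula is the standard normal distribution function of (Z(t) − √t · z) / √(1 − t), where z is the upper 2.5% normal point and t is observed over planned attacks (67 for ITT, 57 for seropositive). Z(t) "will be calculated by the square root of the chi-squared statistic obtained from the aforementioned Cox proportional hazard model", separately in each population.

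The criterion has two parts. The first is that "the calculated predictive power is < 20% in the ITT population; AND", and the second is the same condition in the seropositive cohort. SAP Appendix 2 repeats it more firmly: "The study will be considered futile if the predictive power is < 20% in both the ITT population AND the AQP4-IgG seropositive cohort". Section 5 only says that the study may be declared futile. The Appendix 2 figure "provides estimated predictive power when observed treatment effect varies from 0 to 90% in relative reduction in risk of an AC-determined NMO/NMOSD attack", so it shows benefit only.

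**The concern.** The formula increases with Z(t). It gives the chance of a final result in favour of MEDI-551 only if a harmful trend enters as a negative value. The square root of a chi-squared statistic cannot be negative. Neither SAP Section 5 and Appendix 2 nor Protocol 4.8.10 and Appendix 10 attach a sign or add a rule for an HR above 1.

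Followed literally, the calculation is symmetric around no effect, so a strongly adverse interim result looks promising. Because both populations must fall below 20%, a clearly adverse trend in either one is enough to block the criterion. At stake is whether the rule does its job in a null or harmful trial.

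**Working it through.** **Inputs.** From the SAP: 34 interim and 67 planned attacks (Section 5, Appendix 2), 57 planned seropositive attacks (Section 5), two-sided α = 0.05, 3:1 allocation and target HR 0.4 (Appendix 1).

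**Reproducing the plan's figures.**
- t = 34/67 = 0.5075, √t = 0.712, √(1 − t) = 0.702.
- Z needed for 20% predictive power: 0.712 × 1.960 + 0.702 × (−0.842) = 0.806.
- With the 3:1 null variance, Z = −ln(HR) × √(34 × 3/16) = −ln(HR) × 2.525.
- Cut-off: HR = exp(−0.806/2.525) = 0.727, a 27.3% reduction.
- The same steps give 42.5% at 50% predictive power and 59.7% at 90%.

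Appendix 2 states 27%, 43% and 60%, so this is the plan's own calculation.

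**The adverse side.** Without a sign, only the size of ln(HR) matters. The 20% cut-off therefore recurs at 1/0.727 = 1.376. The event-split variance p(1 − p), with p = 3HR/(3HR + 1), is more realistic away from HR 1 and puts it at 1.42. In the seropositive cohort, assuming 27 to 29 interim attacks, the upper cut-off is 1.39 to 1.41 (1.47 with event-split variance at 29).

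**ITT predictive power at 34 attacks.**

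| Observed HR | Unsigned, null variance | Unsigned, event-split | Unsigned, fitted Cox | Signed |
|---|---|---|---|---|
| 1.5 | 29.8% | 24.5% | 25–27% | below 0.1% |
| 2.0 | 69.3% | 51.0% | 56–58% | below 0.01% |
| 2.5 | 90.4% | 67.8% | 75–78% | below 0.01% |

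Example at HR 2.0, null variance: Z = 0.693 × 2.525 = 1.750, and (1.750 − 1.396)/0.702 = 0.504, which gives 69.3%. With the sign, (−1.750 − 1.396)/0.702 = −4.48.

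**ITT condition alone at a true HR of 1, closed form.** Signed: P(Z < 0.806) = 79%. Unsigned: P(|Z| < 0.806) = 2 × 0.79 − 1 = 58%.

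**Joint rule, simulated.** About 2,500 trials per row, Monte Carlo error about 1 point. From the documents: placebo hazards of 1.5 and 1.0 per year (seropositive, seronegative), 80:20 serostatus, 197-day follow-up, and the two Cox models of Section 5. Assumed: 80 subjects accrued per year, no dropout, constant hazards. Entries are the chance of meeting the futility criterion.

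| True HR | Signed | Unsigned |
|---|---|---|
| 0.4 | 2.9% | 2.8% |
| 1.0 | 72% | 47% |
| 1.25 | 86% | 41% |
| 1.5 | 93% | 32% |
| 2.0 | 98% | 17% |
| 2.5 | 99% | 8% |

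With assumed placebo hazards of 1.0 and 0.67 per year the pairs are 72% and 48% (HR 1.0), 94% and 34% (HR 1.5), 99% and 16% (HR 2.0). A separate bivariate-normal approximation gives about 75% and 49% at HR 1.0, and 98% and 21% at HR 2.0.

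**The case against.** The best defence is that a signed statistic was plainly meant. Section 5 ties the look to the primary analysis, and SAP 3.4.1.3 says an HR below 1 indicates efficacy. Section 5 speaks of the observed trend and an observed Z-statistic, and Appendix 2 scales everything on risk reduction. On that reading the square-root sentence supplies only the magnitude. The intent is very likely so. But 3.4.1.3 explains how to read a hazard ratio and gives no sign to Z(t), while the square-root sentence is the instruction a programmer would follow.

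The second defence is consequence, and much of it stands:
- Protocol 4.8.8 says "An unmasked independent DMC will perform evaluations of safety and clinical outcome data at specified regular intervals throughout the study", so the committee would see the direction of effect. Protocol 4.4 also lets the sponsor stop for adverse events.
- Section 5 and Protocol 4.8.10 word the rule as permissive, although Appendix 2 does not.
- If the drug works, the defect hardly matters. The chance that the ITT statistic lands beyond the mirrored cut-off is under 0.1% at a true HR of 0.4, about 1–2% at 0.6 and about 8% at 0.8. It reaches 21% only at 1.0.
- Events have moved on. SAP 3.4.1.4 records that "the Sponsor received a recommendation from IDMC to stop enrollment and conclude the RCP of the study as early as January 27, 2017", and the protocol's change log says the advice to stop rested on efficacy and safety. The documents do not say whether the 34-attack look was run.

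These points limit the harm. They do not make the calculation correct.

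**Conclusion.** The concern holds: the futility calculation is wrong as specified, not merely short of detail. The ITT condition is met only for an observed HR of about 0.73 to 1.38 (upper limit 1.42 with event-split variance). Null results and mild adverse trends can therefore still meet it, but beyond that limit reported predictive power rises with harm.

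The cut-offs rest only on the SAP's figures and the choice of variance; the SAP does not say which chi-squared is meant. That choice also explains why predictive power at an observed HR of 0.4 is 90% with the null variance, as in Appendix 2, but 96% with the event-split variance. The joint probabilities also depend on the assumed accrual, dropout and hazards, though lower hazards barely change them.

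This should be fixed, but it does not threaten the trial's conclusions: the primary test and Type I error are unaffected, and DMC oversight limits patient risk.

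**What to change.** In SAP Section 5, replace the definition with: Z(t) = −β̂/SE(β̂), where β̂ is the Cox coefficient for MEDI-551 versus placebo, so that positive values favour MEDI-551. State that the 1-df treatment test is used in both populations; this is a clarification, useful because the ITT model also contains serostatus. The 27% cut-off on the benefit side does not move, and the chance of wrongly meeting the criterion at the target HR is essentially unchanged (2.9% against 2.8%).

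Use the same verb for the rule in Section 5 and Appendix 2. If the look has already been run, confirm from the program which statistic was used and file a short note.

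The cost is one SAP sentence and one line of code, plus the note if it applies.

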6 INTER AND INTRARATER RELIABILITY

A study will be conducted to establish inter- and intrarater reliability of the AC members. A random sample of 50% of AC determinations (separately for attack and non-attack) during the RCP will be selected for this purpose. For individual subject thus selected individual rater decision for both original assessment and reassessment time point will be included for this analysis. The intraclass correlation coefficient (ICC) for both inter- and intrarater reliability will be assessed by a random effects model ([Vangeneugden et al.](#)) based on the binary response (attack vs non-attack). The source of individual random effects will be attributed to subject, rater, and time (original vs reassessment). A joint random effect of rater and time will also be included to account for any excess variability. The corresponding statistical model is described below:

$$Y_{prd} = \frac{\exp(\alpha + b_p + b_r + b_d + b_{rd})}{1 + \exp(\alpha + b_p + b_r + b_d + b_{rd})} + \varepsilon_{prd}$$

where b_p, b_r, b_d and b_{rd} are the independent random effects due to subject, rater, time and joint random effect of rater and time distributed as normal with zero mean and variances $\sigma_p^2, \sigma_r^2, \sigma_d^2$ and σ_{rd}^2 respectively. Also ε_{prd} represents an error term normally distributed (independent of other random effects) with mean zero and variance σ_e^2 . The intraclass correlation coefficients are defined as follows:

$$ICC_{\text{Intra}} = \frac{\sigma_p^2 + \sigma_r^2}{\sigma_p^2 + \sigma_r^2 + \sigma_d^2 + \sigma_{rd}^2 + \sigma_e^2} \quad \text{and} \quad ICC_{\text{Inter}} = \frac{\sigma_p^2 + \sigma_d^2}{\sigma_p^2 + \sigma_r^2 + \sigma_d^2 + \sigma_{rd}^2 + \sigma_e^2}$$

The CIs of the ICCs will be calculated based on the method outlined in [Carrasco et al.](#) The standard error of the ICC is obtained by using the delta method:

$$V(\text{ICC}) = \mathbf{d}'\Sigma\mathbf{d}$$

where \mathbf{d} represents the derivatives of ICC with respect to their components denoted by the vector $\boldsymbol{\theta} = (\sigma_p^2, \sigma_r^2, \sigma_d^2, \sigma_{rd}^2, \sigma_e^2)$, $\mathbf{d} = \frac{d}{d\boldsymbol{\theta}}(\text{ICC})$ and Σ is the variance–covariance matrix of the $\boldsymbol{\theta}$. Let, $V_{\text{tot}} = \sigma_p^2 + \sigma_r^2 + \sigma_d^2 + \sigma_{rd}^2 + \sigma_e^2$, then \mathbf{d} will be defined by the following quantities:

$$\frac{d}{d\sigma_p^2}(\text{ICC}_{\text{Intra}}) = \frac{d}{d\sigma_r^2}(\text{ICC}_{\text{Intra}}) = \frac{\sigma_d^2 + \sigma_{rd}^2 + \sigma_e^2}{V_{\text{tot}}^2} = \frac{1 - \text{ICC}_{\text{Intra}}}{V_{\text{tot}}},$$

$$\frac{d}{d\sigma_p^2}(\text{ICC}_{\text{Inter}}) = \frac{d}{d\sigma_d^2}(\text{ICC}_{\text{Inter}}) = \frac{\sigma_r^2 + \sigma_{rd}^2 + \sigma_e^2}{V_{\text{tot}}^2} = \frac{1 - \text{ICC}_{\text{Inter}}}{V_{\text{tot}}},$$

$$\frac{d}{d\sigma_d^2}(\text{ICC}_{\text{Intra}}) = \frac{d}{d\sigma_{rd}^2}(\text{ICC}_{\text{Intra}}) = \frac{d}{d\sigma_e^2}(\text{ICC}_{\text{Intra}}) = -\frac{\sigma_p^2 + \sigma_r^2}{V_{\text{tot}}^2} = -\frac{\text{ICC}_{\text{Intra}}}{V_{\text{tot}}},$$

$$\frac{d}{d\sigma_r^2}(\text{ICC}_{\text{Inter}}) = \frac{d}{d\sigma_{rd}^2}(\text{ICC}_{\text{Inter}}) = \frac{d}{d\sigma_e^2}(\text{ICC}_{\text{Inter}}) = -\frac{\sigma_p^2 + \sigma_d^2}{V_{\text{tot}}^2} = -\frac{\text{ICC}_{\text{Inter}}}{V_{\text{tot}}}.$$

The normal approximation of the estimators of the ICC can be improved by using the inverse hyperbolic tangent transformation $Z = \frac{1}{2} \ln \frac{1 + \text{ICC}}{1 - \text{ICC}}$. Since Z is a function of an asymptotically normal statistic, the delta method can be used to obtain its asymptotic distribution. Thus $\hat{Z} \sim N(0, V(\hat{Z}))$ where $V(\hat{Z})$ is approximated as $V(\hat{Z}) = \frac{V(\text{ICC})}{(1 - \text{ICC}^2)^2}$. Hence the confidence limits for ICC can be estimated by replacing the parameter with their sample counterparts to derive boundaries for Z and transform these bounds as $\frac{\exp(2Z) - 1}{\exp(2Z) + 1}$.

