4.3.1.5 Independent Adjudication Committee

Three experts in NMO/NMOSD disease will constitute the independent AC. This committee has the mandate to evaluate each data set that is generated during the Assessment Visit and determine if an NMO/NMOSD attack occurred based on the clinical presentation, assessments, and the protocol-defined criteria for an NMO/NMOSD attack. The committee is completely independent and blinded to treatment assignments and/or to pertinent treatment

unmasking information (eg, B-cell counts, AQP4-IgG titers post-randomization) of study subjects, and to any decision made by the Principal Investigator regarding an NMO/NMOSD attack. The committee will use its judgement and clinical experience to make its determination based on the data provided. The committee will review the same data that are available to the Principal Investigator when he/she makes his/her determination about the attack. In exceptional cases, determined and justified by the committee as such, the committee can request to review additional data that is essential to make a determination. The committee's role, function and procedures are governed by a separate charter.

The data from all subjects who are assessed at an Assessment Visit due to a new symptom(s) or worsening of an existing symptom(s) related to NMO/NMOSD will be sent for adjudication by the AC regardless of whether the Principal Investigator has determined that an NMO/NMOSD attack has occurred. Furthermore, the AC will not receive information about which protocol attack criterion was met and the rescue medication utilized.

Determination of an NMO/NMOSD attack by the AC is for the purpose of determining which events will be included in the primary analysis. It will NOT affect the rescue therapy that a subject may receive.

Only subjects in whom the attack was determined by the AC will be given the option to enter the OLP.

In addition, the data set that was generated and used by the Principal Investigator to assess the symptom(s) that were determined not to be related to NMO/NMOSD in the RCP, will be delivered to the AC for a non-real-time review.

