4.8.3.2 Additional Analyses of the Primary Endpoint

An estimate of the cumulative event rates through the end of the RCP will be calculated using the Kaplan-Meier (KM) method. Graphical displays of KM estimates and cumulative incidence estimates will be presented by treatment group.

The following sensitivity analyses of the primary endpoint will be performed:

- 1 Analysis using the Cox regression model and the following baseline characteristics and treatment as exploratory variables:
 - Number of NMO/NMOSD relapses prior to randomization
 - Baseline EDSS score
- 2 Analysis similar to primary analysis but considering only unanimous AC-determined NMO/NMOSD attacks (all 3 adjudicators agree) as events, remaining subjects will be considered as censored.
- 3 Analysis similar to primary analysis but also considering subjects who prematurely discontinue the RCP without experiencing an AC-determined NMO/NMOSD attack as treatment failures (events); remaining subjects will be considered as censored.
- 4 Sensitivity analysis will be conducted to assess the impact of the loss of any AC-determined attacks outside of the identified assessment window in the primary analysis.

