4.8.7 Additional Analyses

An exploratory analysis of time to AC-determined NMO/NMOSD attack or rescue therapy without an AC-determined NMO/NMOSD attack during the RCP will be conducted by considering rescue therapy as events of interest as well. Subjects who never experience any AC-determined NMO/NMOSD attack nor receive rescue therapy will be censored for this analysis.

The agreement between site-determined NMO/NMOSD attack and AC- determined NMO/NMOSD attacks will be assessed by Kappa statistic.

An inter- and intra-rater reliability assessment will be performed based on a random selection of all events contributing to the primary analysis.

A shift analysis of the scores from the mRS will be performed.

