3.4.1.4 Additional and Sensitivity Analyses of the Primary Efficacy Endpoint

An estimate of the cumulative event rates at the end of the RCP and median time to event will be calculated using the KM method. Graphical displays of KM estimates and cumulative incidence estimates will be presented by treatment group.

Following sensitivity analyses of the primary endpoint will be performed:

1. Analysis using the Cox regression model with following baseline characteristics and treatment as explanatory variables:
 - Number of prior NMO/NMOSD relapses
 - Baseline EDSS score
2. Analysis similar to primary analysis (attacks from all strata) based on unanimous adjudicated attacks (all three adjudicators agree) as events, remaining subjects will be considered as censored.
3. Analysis similar to primary analysis (attacks from all strata) including subjects who prematurely discontinue the RCP without experiencing an AC-determined attack as treatment failures (events), remaining subjects will be considered as censored.
4. Analysis similar to primary analysis (attacks from all strata) including SFP data for subjects who prematurely discontinue the RCP without experiencing an AC-determined attack. Attack data from the SFP up to 204 days after the subject's initial randomisation will be used in the analysis for subjects who prematurely discontinue the RCP. If the subject did not have an attack in the SFP before or on Day 204 then they will be censored at Day 204.
5. Analysis similar to primary analysis (attacks from all strata) based on only clinical criteria (ie excluding attacks that require MRI dependent criteria), remaining subjects will be considered as censored.
6. The impact of the loss of attacks outside of the attack assessment windows in the primary analysis will be evaluated. The AC-determined attacks falling into different attack assessment windows will be analysed similarly to primary analysis.
 - a. Attacks regardless of attack assessment window;

- b. Attacks with an assessment visit scheduled within 72 hours (3 days) of reporting symptoms and all assessments done within 5 days of an Assessment Visit;
 - c. Attacks with an assessment visit scheduled within 72 hours (3 days) of reporting symptoms regardless whether all assessments are done within 5 days of an Assessment Visit;

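### SAP section 6 leaves the original votes on unsampled adjudications out of both reliability coefficients; adding them would tighten the inter-rater estimate at almost no cost

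*SAP*

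**What the plan says.** SAP section 6 plans a study of how reproducible the AC members' decisions are. The sampling rule is "A random sample of 50% of AC determinations (separately for attack and non-attack) during the RCP will be selected for this purpose". For the selected cases, "individual rater decision for both original assessment and reassessment time point will be included for this analysis". The model is described as follows: "The source of individual random effects will be attributed to subject, rater, and time (original vs reassessment"; a joint rater-by-time effect is then added. Both ICCs come from this single fit, so a determination that is not sampled contributes to neither.

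Protocol section 4.8.7 is shorter: "An inter- and intra-rater reliability assessment will be performed based on a random selection of all events contributing to the primary analysis". It gives no sampling fraction and no reason for sampling.

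Three other statements bear on which votes exist:

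- Protocol section 4.3.1.5: "Three experts in NMO/NMOSD disease will constitute the independent AC".
- SAP section 3.4.1.4, sensitivity analysis 2, repeats the primary analysis "based on unanimous adjudicated attacks (all three adjudicators agree) as events".
- Protocol section 4.8.3.2 has the same analysis, "considering only unanimous AC-determined NMO/NMOSD attacks (all 3 adjudicators agree) as events".

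**The concern.** The two kinds of reliability need different data. Intra-rater reliability needs a second reading, which costs adjudicator time, so a sample is sensible. Inter-rater reliability draws mainly on different members' votes on the same case, and those were cast when the case was first adjudicated. Section 6 applies the sample to both, so about half of the cases that could inform between-rater agreement are set aside although they need no new work.

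The AC determination defines the primary endpoint, and section 6 is the SAP's dedicated study of whether individual members' decisions are reproducible. What is at stake is the width of the confidence interval for the inter-rater ICC, which is wider than the available data require.

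**Working it through.** **The plan's own figures.** Neither document gives a target ICC, a precision or a case count for the reliability study, so there is no such figure to reproduce. The one upstream figure is the number of attacks. With the formula in SAP Appendix 1, (1.960 + 1.282)² / (ln 0.4)² × 16/3 = 66.75, rounded up to 67, as stated.

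**How many cases the sample holds.** The number of non-attack determinations is not given. SAP Appendix 6 mentions 90 investigator-determined attacks as a plausible ceiling, and I use 90 as one assumed total. Half of 67 attacks is about 34, and half of the remaining 23 is 11 or 12, so the sample has about 45 cases.

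**What the re-reads are needed for.** Section 6 defines

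ICC_Inter = (σ²_p + σ²_d) / (σ²_p + σ²_r + σ²_d + σ²_rd + σ²_e),

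for subject (p), rater (r), time (d), rater-by-time (rd) and error (e). With original votes alone there is one time level. Time is then absorbed in the mean, and rater cannot be separated from rater-by-time. The re-read sample is therefore necessary. Original votes on further cases add information on the other components.

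**Precision with and without the unsampled votes.** I treated the section 6 model as linear, with three raters, and compared two data sets:

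- A (SAP): half the cases, both readings.
- B: all original votes, plus re-reads on the same half.

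The expected REML information is I_ij = ½ tr(P K_i P K_j). The variance of the ICC is d′ I⁻¹ d, with the derivatives d given in section 6. All five components are estimated. For 90 cases, with assumed shares of total variance of 0.70 for subject, 0.01 for time, 0.01 for rater-by-time and the remainder for error (ICC_Inter = 0.71):

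| Rater share | SE, A | SE, B | Reduction |
|---|---|---|---|
| 0.005 | 0.0518 | 0.0395 | 24% |
| 0.03 | 0.0568 | 0.0459 | 19% |
| 0.05 | 0.0641 | 0.0547 | 15% |
| 0.10 | 0.0897 | 0.0834 | 7% |

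In the second row the approximate 95% half-width goes from 1.96 × 0.0568 = 0.11 to 1.96 × 0.0459 = 0.09.

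Over 68 to 150 cases and a range of assumed shares, the reduction is about 18 to 25% at rater shares of 0.5 to 2%, 8 to 20% at 5%, and 2 to 14% at 10%. These edges are not sharp. With time and rater-by-time shares of 0.02 each, a rater share of 0.02 and ICC_Inter = 0.82, the reduction is 12 to 17%.

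Doubling the number of cases would suggest 1 − 1/√2 = 29%. The gain is smaller because sampled cases already supply two readings, and because three raters limit what can be learned about rater variance however many cases are added.

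**Bias.** Both strata are sampled at the same 50%, so the mix of attacks and non-attacks is preserved. I simulated binary original votes (67 attacks, 23 non-attacks, 5% vote error, 4,000 runs) and summarised them by Fleiss kappa. Mean kappa was 0.763 with all cases and 0.767 with the stratified half. Kappa is not the SAP's statistic; it serves here only as a check for bias.

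**The case against.** The strongest reply has four parts.

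1. *The protocol itself calls for a random selection*, for inter- and intra-rater reliability together, and section 6 carries this out. That stands: using all original votes goes beyond Protocol section 4.8.7 and should be acknowledged. The SAP already extends that text by sampling non-attacks as well as events.

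2. *A balanced sample with both readings in one model is a coherent design.* This also stands. A reader might infer that the sampling is pointless, or that original votes alone would give the SAP's inter-rater ICC. The documents do not support this, because the ICC contains time and rater-by-time variances that only re-reads can identify. The avoidable part is the exclusion of the unsampled original votes.

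3. *Three individual votes are not documented for every case.* This is partly right. The unanimity analysis needs individual votes only for AC-determined attacks, and AC procedures are left to a separate charter. But section 6 samples non-attacks at random and needs each rater's original decision on whichever is drawn, so those decisions must be retrievable for any of them. That is a strong inference, not a statement in the documents.

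4. *Little depends on the result.* This stands. No ICC threshold is set. The unanimity analysis covers the attacks without sampling, and the agreement analysis between AC and investigator in SAP section 3.4.1.6 is not sampled either. The gain is also smallest when adjudicators differ most, which is when the reliability study would matter most.

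**Conclusion.** The point holds as an efficiency gap. Section 6 confines both ICCs to a random half of the determinations and gives no reason for leaving out original votes already cast on the rest. Including them lowers the standard error of the inter-rater ICC by roughly 20 to 25% when raters differ little, and by about 2 to 14% when rater variance is about 10% of the total. These figures rest on a linear approximation to a binary-response model, assumed variance components and an assumed number of cases; the reduction was positive in every setting tried.

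A reader might infer that the planned ICC is biased or that the primary result is weakened. Neither follows. Sampling is random within attack and non-attack, and this is a supportive analysis on which no primary or key secondary test, alpha or power depends. It is a cheap improvement of low severity.

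**What to change.** - Keep the 50% stratified sample for re-reads.
- Replace the data rule in SAP section 6 with wording such as: *The original votes of all three AC members on all AC determinations during the RCP, together with the re-read votes on the 50% sample, enter the random-effects model; unsampled determinations enter as single-reading cases.* Re-reads are then missing by random design, which a likelihood-based random-effects fit accommodates.
- Confirm from the AC charter or database that individual votes on non-attack determinations are archived. If they are not, apply the extension only where they are, and first consider that adding attacks alone would change the attack/non-attack mix.
- State in the SAP that this extends the random selection described in Protocol section 4.8.7.

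The cost is one or two sentences and one check of the vote records. No extra readings, visits or adjudicator time are needed.
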